9.3 POPULATIONS FOR ANALYSES

To address the primary endpoint of a change in a relative abundance of bacterial taxa approximately 1 month post-BSS compared to baseline (pre-BSS), all participants with a stool sample for microbiome analysis at baseline and at least 1 stool sample for microbiome analysis after BSS treatment will be included.

9.3.1 Evaluable for Toxicity

All participants will be evaluable for toxicity from the time of their first treatment with BSS.

9.4 STATISTICAL ANALYSES

9.4.1 General Approach

The summarized statistics such as mean (for continuous variables) or proportions (for categorical variables) as well as 95% confidence intervals will be provided. More sophisticated statistics will be applied with the microbiome data as below.

9.4.2 Analysis of the Primary Endpoints

In order to quantify changes in the stool microbiome with BSS treatment over a 1-month period, we will examine the following, comparing the baseline microbiome (pre-BSS treatment) with post-treatment samples:

- We will perform Linear discriminant analysis effect size to determine the relative abundance of taxa pre-treatment through approximately 1 month post-treatment. We hypothesize there will be a significant decrease ($p < 0.05$) in certain beneficial taxa (eg, *Lactobacillus*) and increase ($p < 0.05$) in potential pathobionts (eg, *Enterococcus*) post-treatment. Each timepoint post-BSS treatment will be compared to the pre-treatment baseline. If significant differences in the relative abundance of taxa are found in the early time points post-treatment, as per murine models, then we can longitudinally examine post-treatment samples to determine the length of time these differences last.
- We will examine microbial alpha diversity in the stool samples pre-treatment compared to stool samples at each time point through approximately 1 month post-treatment using four different methods (chao1, Shannon diversity index, observed species, PD whole tree).
- We will examine stool sample beta diversity (microbial community structure) pre-treatment compared to post-treatment at each time point over a month using four different methods (unweighted UniFrac, weighted UniFrac, Bray-Curtis dissimilarity, Jaccard distance), and principal coordinate analysis will be used to explore and visualize differences in microbial community structure.

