4.2 SCIENTIFIC RATIONALE FOR STUDY DESIGN

In our murine models, BSS caused a profound effect in the gut microbiome with subsequent changes in the host response. As there are no data on the effect of BSS on the human gut microbiome, an open-label pilot study is needed to gather preliminary data. The study design is strengthened by comparing the microbiome within a same individual before and after intervention as previously reported in other studies of the gut microbiome.(37) Moreover, in our murine models, longitudinal microbiome changes were seen within individual mice, in addition to between control and treatment groups. If an effect is seen, this lays the foundation for confirmation in a study with a randomized control design and further studies to assess the clinical impact and potential health outcomes of these changes in humans.

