9.2 SAMPLE SIZE DETERMINATION

In our laboratory studies (section 2.2), on the day after BSS treatment, the average fold reduction of *Lactobacillus* reads pre- and post-BSS use was 1.57 and the standard deviation (SD) was 0.94. Given the possible larger individual variability and potential overall lower abundance of *Lactobacillus* in humans, for the range of SD between 0.5 to 3, Table 1 below gives the sample size and power calculation to detect a 2-log₁₀ decrease of *Lactobacillus* reads pre- and post-BSS use for type one error of 0.05.

Table 1: Sample size and power calculation

SD	0.5	1	1.5	2	2.5	3
N=20	100%	99.9%	98%	87%	69%	54%
N=15	100%	99.9%	94%	75%	56%	42%

With 20 healthy volunteers, this study has a power 87% to detect the 2-fold change if the standard deviation is 2.

At the end of the study, for the primary endpoint, a paired t-test will be used to calculate the mean log₁₀ change at each post-treatment time point compared to baseline and the 95% confidence interval will be provided. More sophisticated statistics will also be used for the overall microbiome data (section 9.4.2).

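### Section 9.4.2 tests taxa with LEfSe, which does not use the within-person pairing, and the plan does not say whether this or the paired t-test in 9.2 decides the primary endpoint

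*Combined protocol and SAP*

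**What the plan says.** Section 4.2 gives the rationale for a single-arm design: "The study design is strengthened by comparing the microbiome within a same individual before and after intervention". There is no control group, so each person's own baseline is the only comparator.

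Section 9.2 states that "for the primary endpoint, a paired t-test will be used to calculate the mean" log10 change at each visit after treatment, with a 95% confidence interval. The sentence names no taxon. It follows a sample-size calculation for Lactobacillus alone. The next sentence says that further methods, those in section 9.4.2, will be used as well for the microbiome as a whole.

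Section 9.4.2, which is headed as the analysis of the primary endpoints, does not mention the paired t-test. For taxa it says: "We will perform Linear discriminant analysis effect size to determine the relative abundance of taxa pre-treatment through approximately 1 month post-treatment". It then puts p<0.05 on a fall in beneficial taxa, with Lactobacillus as the example, and on a rise in potential pathobionts, with Enterococcus as the example. Each visit after treatment is compared with baseline. No pairing, participant block or participant effect is described.

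**The concern.** LEfSe as usually run screens taxa with Kruskal-Wallis and rank-sum tests between classes of samples and then ranks the survivors by a linear discriminant score. Those tests assume independent samples. Here the baseline class and each later class contain the same people. If a person's level at one visit predicts the level at another, the unpaired tests count stable differences between people as noise, although a within-person comparison would remove them.

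Two things are at stake. First, the taxa tests in 9.4.2 would not hold their nominal 5% level and could miss real within-person shifts. Second, Lactobacillus is tested at the same visits by both methods with no rule for which one counts. If they disagree, the choice could be made after the results are known. For Enterococcus and all other taxa, LEfSe may be the only test that is actually named.

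**Working it through.** **Inputs.** N = 20, effect 2 log10, SD 0.5 to 3 and type I error 0.05 come from section 9.2 ("Table 1 below gives the sample size and power calculation to detect a 2-log"10 decrease, "for the range of SD between 0.5 to 3"). The plan does not say whether the SD is that of the change or of each visit. The within-person correlation ρ is not in the documents, so it is an assumption, examined from 0 to 0.8. The 1-log10 effect is also an assumption, chosen as half the planned effect.

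**Step 1: reproduce Table 1.** A two-sided two-sample t-test with N per group has noncentrality (δ/σ)√(N/2) on 2N − 2 degrees of freedom. For N = 20, δ = 2, σ = 2 this is 1 × √10 = 3.16 on 38 df, so power is 86.9% (stated: 87%). At SD 1.5, 2.5 and 3 it gives 98.4%, 69.3% and 53.8% (stated: 98, 69, 54). For N = 15 at SD 1.5 to 3 it gives 94.1, 75.3, 56.2 and 42.2% (stated: 94, 75, 56, 42).

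The paired t-test named in 9.2, with the SD read as the SD of change, has noncentrality δ√N/SD = 2 × √20/2 = 4.47 on 19 df. That gives 98.9%, not 87%. So Table 1 behaves as an unpaired calculation with a per-visit SD, and the SD is read that way below. The table reproduces with 2 log10 and not with a 2-fold change (0.30 log10), although the sentence under it says "this study has a power 87% to detect the 2-fold change if the standard deviation is 2".

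**Step 2: false-positive rate.** With per-visit SD σ and correlation ρ, the true variance of the mean difference is 2σ²(1 − ρ)/N. An unpaired test assumes 2σ²/N. Its standardised difference is therefore too small by a factor √(1 − ρ). At ρ = 0.5 the 1.96 cut-off acts like 1.96/0.707 = 2.77, which is roughly 0.6% two-sided. Simulation of the Kruskal-Wallis test (20,000 trials, N = 20, normal data) gives about 5% at ρ = 0, 2% at 0.3, 0.8% at 0.5 and 0.1% at 0.7.

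**Step 3: power.** The paired t-test has noncentrality δ√N/(σ√(2(1 − ρ))) on 19 df. At ρ = 0.5 the square root in the denominator is 1, so:
- δ = 2, σ = 2: 2 × 4.472/2 = 4.47, power 99%
- δ = 2, σ = 3: 2 × 4.472/3 = 2.98, power 81%
- δ = 1, σ = 2: 4.472/2 = 2.24, power about 57%

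Simulated power, paired t against unpaired Kruskal-Wallis on the same data:

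| Effect, SD | ρ = 0 | ρ = 0.5 | ρ = 0.8 |
|---|---|---|---|
| 2 log10, SD 2 | 85% vs 85% | 99% vs 92% | 100% vs 98% |
| 2 log10, SD 3 | 52% vs 51% | 81% vs 53% | 99% vs 56% |
| 1 log10, SD 2 | 32% vs 32% | 57% vs 27% | 92% vs 22% |

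Repeat runs move these by about one point; the 27% also came out as 28%.

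The loss comes from ignoring the pairing, not from using ranks. At ρ = 0.5 the signed-rank test, which is paired, gives 98%, 79% and 55% in the same three rows.

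**The case against.** The best reply is that section 9.2 already holds the paired analysis. It assigns the paired t-test to the primary endpoint, with a confidence interval, and introduces 9.4.2 as something done in addition. This stands. A reader might infer that the plan contradicts itself or throws the within-person design away, and the documents do not support that. What remains is that 9.4.2 carries the primary-endpoint heading, applies its own p<0.05 to the same genus at the same visits, and is not ranked against 9.2. The paired sentence in 9.2 could be read to cover every taxon, but it does not say so.

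A second reply is that little power is lost in the plan's own scenario. At 2 log10 and SD 2 the gap is 0 to about 7 points over ρ from 0 to 0.8, and the unpaired test still roughly delivers the advertised 87%. This stands too, so an inference that most of the power is lost is not supported in general. However, that scenario leans on mouse data from the day after treatment ("the average fold reduction of *Lactobacillus* reads pre- and post-BSS use was 1.57 and the standard deviation (SD) was 0.94"). The endpoint is about one month, and section 9.1 expects the effect to be strongest at day 2 with only some changes lasting. Smaller effects are therefore plausible, and there the gap is wide if ρ is substantial.

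Third, the error is conservative, so it does not create false claims. That is correct for positively correlated samples.

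A reader might also add that shares of reads are compositional, so a large rise in one genus dilutes the others. That is a separate matter from pairing, and its size depends on a starting share that the documents do not give.

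**Conclusion.** The point holds as a problem of method and of clarity. The taxa analysis in 9.4.2 as written does not use the pairing that section 4.2 relies on, and nothing in the plan says whether it or the paired t-test in 9.2 decides. At an assumed correlation of 0.5 the unpaired test rejects under 1% instead of 5% when there is no effect. The power cost is 7 points at 2 log10 and SD 2, 28 points at 2 log10 and SD 3, and about 30 points at 1 log10 and SD 2. At correlation 0 there is no cost.

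These figures assume normal data, one taxon and 20 complete pairs. Zero counts, the discriminant-score cut-off and multiplicity across taxa were not modelled.

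This should be fixed, but it is not a critical flaw: the study is an exploratory pilot, a paired test is already in the plan, and the miscalibration does not inflate false positives.

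**What to change.** - State in 9.4.2 that the paired within-person log-change analysis of section 9.2 (paired t or signed-rank) decides the primary endpoint for Lactobacillus and Enterococcus.
- Test the remaining taxa with a paired or participant-blocked method, for example signed-rank, or a mixed model with a participant effect.
- Keep LEfSe as a descriptive display, without a decisive p-value.
- While editing 9.2, say whether the SD in Table 1 is per visit or of the change, and recompute the table for the paired test.

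The cost is a few sentences and standard software. No new data, visits or participants are needed. The change should be made before results are seen.

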4 STUDY DESIGN

4.1 OVERALL DESIGN

This is an exploratory, single-site, single-arm, open-label study of the effects of BSS on the human gut microbiome and host response. It is hypothesized that there will be a decrease in

beneficial bacterial taxa (eg, *Lactobacillus*) and increase in potential pathobionts (eg, *Enterococcus*) as seen in murine models (section 2.2).

Upon confirmation of eligibility, healthy adult volunteers (n=20) will undergo baseline assessment of gut microbiome and host response by providing a stool sample. Participants also have the option to provide blood, urine, and saliva, and to undergo colonoscopy for collection of biopsies and brushings. Approximately 1 to 18 weeks later, they will provide another stool sample (with optional blood, urine, and saliva), and then begin a brief regimen of BSS: 1050 mg 4 times daily (about 1 to 6 hours apart) for 2 days. Remote or in-person follow-up visits will be at days 2 (+3), 8 (± 3), 14 ($-3/+7$), and 28 (± 7). Participants will be assessed for AEs and provide stool samples, and have the option to provide blood, urine, and saliva. Participants may also have a second colonoscopy with collection of biopsies and brushings at the day 8 follow-up visit.

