8.2.1 Biospecimen Evaluations

Stool: Stool is the only required sample and will be collected at all study visits. For remote visits, participants will be provided with an at-home collection kit, which they can ship to the NIH. Participants may not be able to provide a stool sample at all visits. The minimum number of samples required for this study (ie, that does not constitute a protocol deviation, section 10.9) is 1 sample before starting the BSS regimen and 1 sample after completion of the regimen. Research evaluations on stool samples will include the following:

- Microbiome sequencing (including 16S ribosomal [r]RNA gene sequencing, shotgun metagenomic sequencing and evaluation of the resistome, virome, and parasitome).
- Metabolomics to evaluate intestinal metabolomic profiles, and when combined with microbiome/metagenomic studies, may suggest some functional role for candidate microbes of interest.
- Fecal flow (sorting and 16S and/or shotgun sequencing of immunoglobulin [Ig]A-bound organisms, which is an indication of pathogenicity).
- Lipocalin, calprotectin, and α -1-anti-trypsin levels (to evaluate mucosal inflammation and malabsorption).
- Measurement of secreted IgA and antimicrobial peptides.
- Culturing/polymerase chain reaction for specific organisms.
- Stool proteomics.
- Use of stool samples in murine models.
- Metatranscriptomics (the gene expression of the microbiota and host).
- Storage for future research.

Blood: Blood is an optional sample that will only be collected at in-person visits. Between 30 to 150 mL of blood will be collected per visit. The amount of blood drawn for research purposes will be within the limits allowed for adult research participants by the NIH CC (Medical Administrative Policy 95-9, Guidelines for Limits of Blood Drawn for Research Purposes in the Clinical Center: <http://cc-internal.cc.nih.gov/policies/PDF/M95-9.pdf>). Research evaluations on blood include the following:

- Host immune and inflammatory responses, and specific responses to the microbiome.
- Metabolomics.
- Lipopolysaccharide and lipopolysaccharide-binding protein (for evaluation of bacterial translocation and intestinal permeability).

Abbreviated Title: BSS Gut Microbiome

Version Date: 05 July 2024

- Isolation and cryopreservation of peripheral blood mononuclear cells and serum (for the creation of induced pluripotent stem [iPS] cells and future evaluation of systemic immune responses).

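### Taxa are tested at p<0.05 across an open list and four visits, with no multiplicity control, closed taxa list or lead visit for testing

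*Combined protocol and SAP*

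**What the plan says.** Section 9.4.2 names the taxon-level method: "We will perform Linear discriminant analysis effect size to determine the relative abundance of taxa". The expected result follows: "We hypothesize there will be a significant decrease ($p < 0.05$) in certain beneficial taxa", and a rise at the same threshold in potential pathobionts. One genus is given as an example of each class. On timing: "Each timepoint post-BSS treatment will be compared to the pre-treatment baseline". Section 4.1 and the schedule of activities set four such visits, at days 2, 8, 14 and 28.

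Alpha diversity is examined at each visit "using four different methods (chao1, Shannon diversity index, observed species, PD whole tree"), and beta diversity by four distance measures, with principal coordinate analysis for exploration and display. No test or threshold is attached to either set, and no metric leads.

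Section 9.2 sizes the study on *Lactobacillus* alone, "pre- and post-BSS use for type one error of 0.05", and plans a paired t-test with a 95% confidence interval at every post-treatment visit. Section 9.4.1 adds only "More sophisticated statistics will be applied with the microbiome data as below".

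Section 9 does not mention multiplicity, false discovery rate, a testing order, a taxonomic rank, a prevalence filter or an LDA cut-off. Section 8.2.1 leaves the sequencing scope wide: 16S and "shotgun metagenomic sequencing and evaluation of the resistome, virome, and parasitome".

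**The concern.** The only numerical criterion given for a taxon is p<0.05, and it applies to a list that can grow after the data are seen. Read literally, a fall in any taxon that can be called beneficial, or a rise in any that can be called a pathobiont, at any of four visits, would fit the hypothesis. The endpoint in sections 1.1 and 3 points to about one month. Section 9.1, however, expects the largest change at day 2, and sections 9.2 and 9.4.2 test every visit, so no visit leads the testing.

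The 0.05 type I error used for sizing describes one test of one genus. It does not describe the chance that the study reports some change when there is none. Sections 2.1 and 4.2 say that a seen effect would be the basis for further studies, and nothing beyond p<0.05 defines seen. With a single arm, no concurrent control group can show how many such changes arise by chance.

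**Working it through.** **Inputs from the documents.** Threshold 0.05 (9.2, 9.4.2); four post-treatment visits (4.1); four alpha and four beta metrics (9.4.2); N=20, difference 2 log10, SD 2, power 87% (9.2, Table 1). **Assumed:** the number of taxa m, which the documents do not give. The main range is 50 to 200; 10 and 500 are shown as extremes.

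**1. The plan's own figure.** Noncentral-t power, two-sided 0.05, difference 2.
- Two-sample test with N per group, N=20, SD 1.5 / 2 / 2.5 / 3: 98.4 / 86.9 / 69.3 / 53.8%. Table 1 has 98 / 87 / 69 / 54%.
- The same with N=15: 94.1 / 75.3 / 56.2 / 42.2%. Table 1 has 94 / 75 / 56 / 42%.
- The paired test that section 9.2 names, with SD taken as the SD of the change, gives 98.9% at N=20, SD 2, so Table 1 rests on an unpaired calculation. That is a separate matter, but it means the cost of any adjustment has to be shown on both bases.

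**2. Expected false taxon-by-visit findings when BSS has no effect.** Formula: m × 4 × 0.05, for correctly sized tests.

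| Taxa (assumed) | Tests | Expected false findings |
|---|---|---|
| 10 | 40 | 2 |
| 20 | 80 | 4 |
| 50 | 200 | 10 |
| 100 | 400 | 20 |
| 200 | 800 | 40 |
| 500 | 2,000 | 100 |

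Correlation between tests does not change these means. They count all taxa and both directions.

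**3. Chance of at least one.** One taxon, four independent tests: 1 − 0.95^4 = 18.5%. The visits share one baseline, which lowers this. Simulating paired t-tests with n=20 and a common baseline gives about 16%. For independent taxa, 1 − 0.84^10 = 0.83 with 10 taxa and 1 − 0.84^20 = 0.97 with 20.

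**4. If LEfSe compares pre and post samples as unpaired groups.** Section 9.4.2 does not say. At an assumed within-person correlation of 0.5, the true error rate is about 0.006 per test: 400 × 0.006 ≈ 2.4 false findings for 100 taxa and 800 × 0.006 ≈ 4.8 for 200 (simulated 3.0 and 6.1). An LDA cut-off would lower the count further, but none is stated.

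**5. Diversity metrics, if each were tested at 0.05.** (4 + 4) × 4 = 32 comparisons; 32 × 0.05 = 1.6 expected. Under independence the chance of at least one is 1 − 0.95^32 = 80.6%. The metrics are correlated, so this is an upper figure. With an assumed correlation of 0.5 between visits and 0.5 to 0.9 between metrics, simulation gives about 67% down to 47%.

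**6. With Benjamini-Hochberg at 5%.** Over all taxon-by-visit tests, with 50 to 200 taxa, the simulated chance of any false finding under no effect is about 4 to 6%.

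**The case against.** The plan is silent on correction; it does not say that the tests will be uncorrected. Nor does it say that every taxon is judged by p<0.05 alone: the threshold sits in a hypothesis sentence about some taxa, and the named method also ranks by effect size. Both points stand. The silence still leaves uncorrected reporting open, and the effect-size component has no stated cut-off that could act as a filter.

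A reader might infer that dozens of false findings are to be expected. The documents do not support that as a fact. Reaching 24 takes 24 / (4 × 0.05) = 120 taxa, or (24 / 0.05 − 32) / 4 = 112 if the diversity comparisons are counted, and the tests must be correctly sized. The number that would seem to confirm the hypothesis is also smaller than the totals above, because only changes in the expected direction and class count. It cannot be computed without a classification of taxa.

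The strongest objection is purpose. The study calls itself exploratory, section 4.2 calls it a pilot for preliminary data, and confirmation is left to a randomized study. It would be too strong to say that a positive result automatically triggers that study; the text says it lays a foundation. Section 9.2 also provides confidence intervals, so results will not rest on p-values alone. This lowers the severity. It does not remove the point, because section 9 also states a hypothesis, a type I error, a power and a significance threshold, and that error rate cannot hold over an open list at four visits.

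**Conclusion.** The point holds as a gap in the taxon-level primary analysis: an open set of taxa, four visits, p<0.05, and no multiplicity control, closed list or lead visit for testing. With an assumed 50 to 200 taxa and correctly sized tests, about 10 to 40 false taxon-by-visit findings are expected if BSS does nothing. At least one is near certain (about 97%, independent taxa) with only 20 taxa, so the conclusion does not hang on a large taxon count. The expected number is lower if samples are compared unpaired or an LDA cut-off is used.

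The diversity metrics are a minor part. A reader might take p<0.05 to govern them too, but section 9.4.2 attaches no test or threshold to them. At 0.05 they would add about 1.6 expected false positives, with at most about an 81% chance of at least one.

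For an exploratory pilot with confirmation deferred, this should be fixed and is cheap to fix; it does not invalidate the study.

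**What to change.** In section 9.4.2, before any sequencing data are examined:

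- Name *Lactobacillus* and *Enterococcus* as the two lead taxa at one prespecified visit, with Holm adjustment at two-sided 0.05.
- Report all other taxon-by-visit tests with Benjamini-Hochberg at q<0.05, labelled exploratory. To fix that family, state the taxonomic rank, any prevalence filter, the LDA cut-off and whether the test is paired.
- Name one lead alpha and one lead beta metric, of the team's choice, with the others as supportive.

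Cost: wording only, with no extra participants or samples. Fewer taxa will be called significant. At the Bonferroni bound (alpha 0.05 / 2 = 0.025), power per lead taxon for N=20, difference 2 and SD 2 (d=1) falls from 98.9% to 97.3% with the planned paired test, or from 86.9% to 79.3% on the unpaired basis that reproduces Table 1. Holm loses no more than this.
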